#### Derivation of the rate for sero-conversion for the historical controls

Historical controls are estimated from cure rates presented in two publications [1][2]. The historical placebo cure rate used is shown in Table 6–1:

#### Table 6–1: Historical Cure Rates for Placebo

Publication	Age range (in years)	Sero-conversion rate (95%Cl) in placebo patients
de Andrade et al 1996	7-12	3/65 = 5% (1%,13%)
Sosa et al 1998	6 -12	2/44= 5% (1%,16%)

Both publications show a 5% cure rate for the placebo group. For the primary objective in our study, superiority over placebo will be confirmed if the lower limit of the 95% CI for the nifurtimox (60-day regimen) cure rate is greater than 16%, the larger of the upper limits of the 95% CIs from the two publications.

#### Primary analysis of the primary efficacy variable

The difference in the proportion of nifurtimox subjects with sero-reduction or sero-conversion (60-day regimen) and the proportion estimated from historical data will be tested using an asymptotic 2-sided 95% CI with a continuity correction of 1/2n for a single proportion.

The null hypothesis  $H_0$  is  $p_{nifurtimox} = p_{placebo}$ 

The alternative hypothesis H1 is  $p_{nifurtimox} \neq p_{placebo}$ , where pt is the cure rate for treatment t.

Superiority will be confirmed if the lower limit of the CI for the proportion of nifurtimox subjects (60-day regimen) with sero-reduction or sero-conversion is greater than 16%. The proportion and asymptotic 2-sided limits ( $p_l$ ,  $p_u$ ) of the 95% CI for  $p_{nifurtimox}$  can be computed by [3]

$$\hat{p}_{nifurtimox} = x/n$$

$$p_u = \hat{p}_{nifurtimos} + 1.96 \sqrt{\hat{p}_{nifurtimos}(1 - \hat{p}_{nifurtimos})/n} + 1/2n$$

$$p_l = \hat{p}_{nifurtimox} - 1.96 \sqrt{\hat{p}_{nifurtimox}(1 - \hat{p}_{nifurtimox})/n} - 1/2n$$

where x denotes the number of nifurtimox subjects with sero-reduction or sero-conversion and n the total number of subjects in 60-day regimen group. The SAS code will be:

PROC FREQ;

TABLES cured / BINOMIALC;

WEIGHT counts;

RUN;

#### Secondary analysis of the primary efficacy variable

A secondary analysis will be done to compare the proportion of subjects with sero-reduction or sero-conversion for the 60-day and 30-day nifurtimox regimens. This will be performed using an asymptotic 2-sided 95% CI for the difference of two independent proportions.

The null hypothesis  $H_0$  is  $p_{nifurtimox, 60d} = p_{nifurtimox, 30d}$ 

The alternative hypothesis H1 is  $p_{nifurtimox, 60d} \neq p_{nifurtimox, 30d}$ , where  $p_t$  is the cure rate for treatment *t*.

Difference in efficacy between the two groups will be confirmed if the CI for the difference of two proportions of nifurtimox subjects (60-day regimen *versus* 30-day regimen) with sero-reduction or sero-conversion does not include 0. The proportions and asymptotic 2-sided limits ( $l_l$ ,  $l_u$ ) of the 95% CI for *pnifurtimox*, 60d - *pnifurtimox*, 30d can be obtained by [3]

$$\begin{split} \hat{p}_{i} &= \frac{x_{i}}{n_{i}}, \qquad i = 1, 2. \\ l_{u} &= (\hat{p}_{1} - \hat{p}_{2}) + 1.96\sqrt{(\hat{p}_{1}(1 - \hat{p}_{1})/n_{1}) + (\hat{p}_{2}(1 - \hat{p}_{2})/n_{2})} + \frac{1}{2} \left(\frac{1}{n_{1}} + \frac{1}{n_{2}}\right) \\ l_{l} &= (\hat{p}_{1} - \hat{p}_{2}) - 1.96\sqrt{(\hat{p}_{1}(1 - \hat{p}_{1})/n_{1}) + (\hat{p}_{2}(1 - \hat{p}_{2})/n_{2})} - \frac{1}{2} \left(\frac{1}{n_{1}} + \frac{1}{n_{2}}\right) \end{split}$$

where  $p_i$ ,  $x_i$  and  $n_i$  denote the cure rate, the number of nifurtimox subjects with sero-reduction or sero-conversion, and the total number of subjects, for treatment *i* respectively. Treatment *i*=1, 2 represents 60-day and 30-day nifurtimox regimens, respectively.

The SAS code will be:

*Reference Number: BPD-SOP-060 Supplement Version: 6* 

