A minimum of 38 subjects in each age stratum is targeted, but not required, in order to be able to derive meaningful safety conclusions. Enrollment may⁵³ continue until this specification is met, unless it is determined that such a target would be unlikely to be reached in a reasonable time.⁵⁴

No study-specific procedures will be performed before the subject/legally authorized representative has signed the informed consent form, or a minor subject has provided assent, including asking a potential subject to fast (if applicable, depending on the age of the subject at the discretion of the investigator) prior to the screening blood samples. Informed consent/assent for optional PK blood sampling will also be obtained. After the consents/assents have been obtained, screening assessments will be performed from 1 to 14 days prior to randomization at Visit 2.⁵⁵

After study eligibility has been confirmed and safety assessments have been performed at Visit 2 (Day 1),⁵⁶ subjects will be randomized via Interactive Voice Response System/Interactive Web Response System (IVRS/IWRS) in a 2:1 ratio (60-day regimen vs. 30-day regimen) to one of two treatment groups:

- Nifurtimox tablets administered three times daily for 60 days (Days 1 60, active nifurtimox treatment, Treatment Group 1) or
- Nifurtimox tablets administered three times daily for 30 days, followed by nifurtimox placebo administered three times daily for 30 days (Days 1 30, active nifurtimox treatment; Days 31 60, placebo; Treatment Group 2).

The first dose of study drug will be administered at Visit 2. Pre- and post-dose PK blood samples will be obtained at specified time points from those subjects consenting to PK assessments (see Table 9–1). At the 2 – 4 hour time point of PK blood sampling (i.e., at the time of maximum concentration $[C_{max}]$), an ECG (optional for subjects < 5 years of age at the discretion of the investigator) will be obtained to allow for PK/PD investigations. Study drug

 $^{^{50}}$ Modified as per amendment 2

⁵¹ Text modified for clarity (Amendment 1)

 $^{^{52}}$ Cohort replaced with stratum throughout body of protocol as per amendment 2

⁵³ Text modified as per amendment 4

⁵⁴ Text added as per amendment 2

⁵⁵ Text added for clarity (Amendment 1)

⁵⁶ Text modified for clarity (Amendment 1)

	Integrated Clinical Study Protocol BAY A2502 / 16027	
03 NOV 2020	Version 11.0	Page: 29 of 259

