Alternative and more rapid approaches as an early indicator of negative sero-conversion in treated patients have been suggested. Using non-conventional serological techniques, i.e., highly sensitive and specific chemiluminescent ELISA using a purified trypomastigote glycoconjugate antigen and an epimastigote complex [20], the time to negativization was significantly sooner for the non-conventional ELISA than for the conventional ELISA. The chemiluminescent ELISAs provide tests that are highly sensitive and specific for Chagas' disease diagnosis. They can be used in blood bank screening and to monitor the treatment of patients undergoing chemotherapy [21].⁷⁶

Non-conventional ELISA antigens, such as those used in the Sosa-Estani and deAndrade trials (i.e., F29 and F 2/3), [15][16] are often considered as early markers for effective Chagas' disease therapy. In the study by Altcheh, et al, the kinetics of disappearance of conventional serology and anti-F2/3 antibodies were compared in 21 patients with congenital Chagas' disease after receiving benznidazole treatment. Patients were divided into two groups: (A) age < 8 months at diagnosis and (B) age > 9 months at diagnosis. Group A presented negative outcome for conventional serology at 6.6 months (CI 95 3.4-9.8 months) and for anti-F2/3 at 4 months (CI 95 0.9-7.1 months, p = 0.18). Group B exhibited nonreactive conventional serology at 63.1 months (CI 95 42.1-84.2 months) whereas anti-F2/3 antibody determination became negative at 21.9 months (CI 95 5.7-38.1 months, p = 0.0025). In patients belonging to Group A, antibodies were undetectable by both conventional serology and anti-F2/3 ELISA soon after receiving chemotherapy. In infants included in Group B, a negative result for anti-F2/3 antibody detection occurred significantly in advance of negative conventional serology reactivity. Consequently, the anti-F2/3 antibody assay becoming negative should be considered as a surrogate endpoint for assessment of cure or positive response to treatment, particularly in those patients with prolonged time of infection [18].

A new perspective on Chagas' disease diagnosis was opened by the use of the PCR as a measure of treatment response. Over the past few years, the availability of PCR to detect *T. cruzi* DNA in blood samples has opened new possibilities for the evaluation of response to trypanocidal chemotherapy.⁷⁷

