Clearance of parasitemia (evaluated most commonly by xenodiagnoses or PCR) combined with disappearance of antibodies (seronegative conversion) has been proposed as cure criteria by some authors.[19] The main limitations in evaluating treatment response for Chagas' disease using conventional serology stems from the need for long-term follow-up (years to decades) to observe negativization of conventional serological tests.⁷⁸

⁷⁵ Term "titer(s)" replaced with "concentration(s)"; text modified for clarity (Amendment 1)

⁷⁶ Paragraph added to include updated information (Amendment 1)

⁷⁷ Paragraphs added to include updated information (Amendment 1)

⁷⁸ Text deleted from end of paragraph and moved to appear earlier in this section (Amendment 1)

	Integrated Clinical Study Protocol	
	BAY A2502 / 16027	
03 NOV 2020	Version 11.0	Page: 33 of 259

In the experience of Parasitology service, Ricardo Gutierrez Children's Hospital, Buenos Aires unpublished data (presented at European Society of Pediatric Infectious Disease 2014 and meeting of Food and Drug Administration) by PPD, a correlation between negativization of conventional serology (whole antibody against *T. cruzi* measured by ELISA or hemoagglutination inhibition) and PCR results in children 2 years of age and younger is fairly high; the correlation between these two tests in children older than 3 years is lower, as sero-conversion (i.e., becoming negative) may take several years, while PCR becomes negative within 60 days of treatment, and remains negative in this age group also. In the whole population, at least 20% sero-reduction of conventional serology was observed at 12 months. This percentage was higher in the younger children than in the older children.⁷⁹

By comparing 48 PCR methods from 26 laboratories, it was shown that the four best performing methods showed a high sensitivity (10 fg/ μ l DNA and 0.5 parasites/mL blood), and an overall accuracy of 87% to 90% [22]. More recent publications showed comparable sensitivity [23][24].

Several studies concluded that PCR has a higher sensitivity for detecting therapeutic failures compared to usual parasitological and conventional serologic methods. However, only two demonstrated specificity and showed that PCR could be used as a tool for early determination of cure [25][26].

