## 3. Study Design

## 3.1 Part 1 (CHICO)

## **Design overview**

#### BAY No. A2502/IMPACT No. 16027 Page: 7 of 30

This is a Phase 3, prospective, randomized (to dosing regimen), age-stratified, double-blind, parallel-group study to evaluate the efficacy, safety/tolerability, and PK of oral administration of nifurtimox in children with a diagnosis of Chagas' disease. A schematic of the study design is presented in Figure 3-1.

#### Figure 3–1. Study Design of Part 1

D = Day, EOT = end-of-treatment, V = Visit.

a At Visits 4, 5, and 7, study site personnel will contact the subject/legally authorized representative via telephone to assess for the occurrence of AEs, use of concomitant medications, and compliance with study drug administration. If any safety concern arises, subjects may return to the study site for an Unscheduled Visit.
b Subjects who discontinue prematurely from study drug administration will continue to return to the investigational site for study assessments at Visits 3, 6, and 8 (EOT), and undergo telephone assessments as described for Visits 4, 5, and 7. If subjects are unable/unwilling to do so, they must return to the investigational site 30 (±3) days after the last dose of study drug for EOT (Visit 8) assessments, and undergo telephone assessments as described for Visits 4, 5, and 7. If the subject is unable/unwilling to return to the clinic for the EOT Visit 8), then a telephone assessment as described for Visits 4, 5, and 7. If subjects is unable/unwilling to return to the clinic for the EOT Visit 8), then a telephone

assessment as described for Visits 4, 5, and 7 may be performed in lieu of Visit 8 assessments.

In this study, approximately 300 pediatric subjects will be randomized (2:1 randomization, 60-day regimen vs. 30-day regimen). Subjects will be stratified by age at randomization into four strata as specified below:

- Stratum 1: 0 to 27 days
- Stratum 2: 28 days to younger than 8 months
- Stratum 3: 8 months to younger than 2 years
- Stratum 4: 2 years to younger than 18 years

A minimum of 38 subjects in each age stratum is targeted, but not required, in order to be able to derive meaningful safety conclusions. Enrollment will continue until this specification is

met, unless it is determined that such a target would be unlikely to be reached in a reasonable time.

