#### PROC FREQ;

TABLES group\*cured / RISKDIFFC;

WEIGHT counts;

RUN;

The analyses specified above (the proportion of subjects with sero-reduction or seroconversion and an asymptotic 95% CI for the 60-day nifurtimox regimen, and the difference of two independent proportions for the 60-day and 30-day regimens and an asymptotic 95% CI) will also be done using data from Days 7 (Visit 3), Days 30 (Visit 6), the EOT visit (Visit 8), and Days 240 (Visit 10). In the event of small sample sizes for the subgroups, an exact 95% CI will be calculated instead of an asymptotic one.

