## Subgroup analyses of the primary efficacy variable

The proportion of nifurtimox subjects with sero-reduction or sero-conversion (60-day regimen) and an asymptotic 2-sided 95% CI for the proportion will be calculated by country and for each age stratum.

The same proportion and an asymptotic 2-sided 95% CI for the difference of the 60-day and 30-day nifurtimox regimens will also be summarized by country and for each age stratum.

BAY No. A2502/IMPACT No. 16027

Page:

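### The randomised 60-day versus 30-day comparison ignores the age strata used for randomisation, so its CI is wider than needed if cure rates differ by age

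*SAP*

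**What the plan says.** SAP 3.1 (Design overview) describes 2:1 randomisation of about 300 children and says: "Subjects will be stratified by age at randomization into four strata as specified below". The strata are 0 to 27 days, 28 days to under 8 months, 8 months to under 2 years, and 2 to under 18 years. On stratum size, Protocol 5.1 (Design overview) says: "A minimum of 38 subjects in each age stratum is targeted, but not required".

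For 60 versus 30 days, SAP 6.2.1.1 (Secondary analysis of the primary efficacy variable) says: "This will be performed using an asymptotic 2-sided 95% CI for the difference of two independent proportions". The estimate is the difference of the two crude proportions. The interval is a continuity-corrected Wald interval, and the SAS code is a two-way table of group by cure with no stratum variable. The decision rule is: "Difference in efficacy between the two groups will be confirmed if the CI for the difference of two proportions of nifurtimox subjects" excludes zero. The same analysis is repeated at Visits 3, 6, 8 and 10, with this provision: "In the event of small sample sizes for the subgroups, an exact 95% CI will be calculated instead of an asymptotic one".

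Under Subgroup analyses of the primary efficacy variable, the 60-day minus 30-day difference "will also be summarized by country and for each age stratum". No age-adjusted overall estimate is planned. Protocol 10.3.2.1 asks only for a two-sided 95% CI for a difference of two independent proportions and leaves the detail to the SAP.

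**The concern.** When randomisation is stratified by a factor that predicts outcome, the arms are balanced on that factor by design. A pooled binomial variance does not credit that balance. It counts variation in cure between age groups as if it were noise in the comparison, so the interval is too wide.

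The protocol gives reason to expect age to matter. In the congenital benznidazole series cited in Protocol 5.1 (Justification of the design), conventional serology became negative at 6.6 months in children under 8 months at diagnosis. In the older group: "Group B exhibited nonreactive conventional serology at 63.1 months". Of unpublished hospital data on sero-reduction of at least 20% at 12 months, the protocol says: "This percentage was higher in the younger children than in the older children". The definition of cure also changes at 8 months, the boundary between strata 2 and 3: below that age only sero-conversion counts.

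This is the overall randomised comparison of the two regimens on the primary endpoint, and the size of the 30-day arm rests on CI width alone (Protocol 10.4). Because a difference is declared only when the interval excludes zero, excess width makes it easier to miss a real loss of efficacy with the shorter course.

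**Working it through.** **Inputs from the documents.** Arm sizes are 200 and 100 and the planning cure rate is 55% (Protocol 10.4). Allocation is 2:1 within four strata, with 38 per stratum as a target only. SAP 6.5 still quotes 260 and 130 for Part 1, but SAP 3.1 says about 300, so 200/100 is used here.

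**Inputs assumed.** The documents give no cure rates by stratum on the composite endpoint. All stratum rates below are assumptions, as are all stratum sizes other than 38. Strata of 38/38/38 leave 300 − 114 = 186 in stratum 4.

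**Step 1: reproduce the plan's figure.** Half-width = 1.96 × √[p(1−p)(1/200 + 1/100)]. At p = 0.55 this is 1.96 × √(0.2475 × 0.015) = 0.119, which matches the protocol's approximate 0.12. The SAP's continuity term is 0.5 × (1/200 + 1/100) = 0.0075, so the interval actually specified has a half-width of 0.127.

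**Step 2: stratified half-width.** The Mantel-Haenszel weights are w_s ∝ n1s·n2s/(n1s + n2s), and the variance is Σ w_s²[p1s(1−p1s)/n1s + p2s(1−p2s)/n2s]. With 2:1 allocation in every stratum and no arm difference, this reduces to 0.015 × Σ N_s p_s(1−p_s)/300.

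Example, rates 0.8/0.8/0.6/0.45:
- Stratified: Σ N_s p_s(1−p_s)/300 = (6.08 + 6.08 + 9.12 + 46.035)/300 = 0.2244. Half-width 1.96 × √(0.2244 × 0.015) = 0.1137.
- Pooled: overall rate 0.5577, so p(1−p) = 0.2467. Half-width 1.96 × √(0.2467 × 0.015) = 0.1192.
- Cut: 1 − 0.1137/0.1192 = 4.6%.

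**Step 3: power.** For an assumed 15-point loss in every stratum, with the continuity term kept in both methods, power = Φ((0.15 − 0.0075)/SE − 1.96). In the flat case, pooled SE = √(0.55×0.45/200 + 0.40×0.60/100) = 0.0603, so power is Φ(0.40) = 0.656.

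Results with strata 38/38/38/186 (half-widths before the continuity term):

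| Assumed cure rates, strata 1–4 | Pooled | Stratified | Cut | Power, pooled to stratified |
|---|---|---|---|---|
| 0.55 throughout | 0.1194 | 0.1194 | 0% | 0.656 to 0.656 |
| 0.65/0.65/0.60/0.50 | 0.1194 | 0.1183 | 0.9% | 0.656 to 0.664 |
| 0.8/0.8/0.6/0.45 | 0.1192 | 0.1137 | 4.6% | 0.655 to 0.697 |
| 0.9/0.9/0.6/0.4 | 0.1194 | 0.1079 | 9.6% | 0.656 to 0.745 |
| 0.9/0.9/0.7/0.3 | 0.1200 | 0.1017 | 15.2% | 0.669 to 0.817 |
| 0.4/0.4/0.6/0.6 (infants worse) | 0.1194 | 0.1176 | 1.5% | 0.657 to 0.670 |

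**Step 4: fewer infants.** Keeping the same stratum rates:
- Strata 15/25/38/222: the 4.6%, 9.6% and 15.2% cuts become 3.0%, 6.2% and 11.0%. Power by the same formula goes from 0.665 to 0.693, 0.673 to 0.732, and 0.706 to 0.817.
- Strata 10/20/38/232: the cuts become 2.5%, 5.0% and 9.6%. Power goes from 0.669 to 0.692, 0.680 to 0.729, and 0.720 to 0.817.
- The mild gradient gives 0.6% in both.

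**Step 5: coverage.** Simulation used 40,000 trials per scenario, flat to steep gradients, and a true difference of 0 or 0.15. The SAP interval covered 0.959 to 0.986. The Mantel-Haenszel interval with the Sato variance and no continuity term covered 0.945 to 0.949. Separate runs that summed the stratum binomial variances gave 0.943 to 0.947. With flat rates the SAP interval already covers about 0.960, which comes from the continuity term and not from pooling.

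**The case against.** This is a matter of efficiency only. The pooled estimate is unbiased under balanced 2:1 allocation, its interval is conservative, and the plan delivers the half-width it promised. The by-stratum differences will also show any age pattern. All of that stands.

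The age gradient on the composite endpoint is not established. One source is time to negative serology in 21 congenital cases on another drug. The other is unpublished, gives no size, and concerns sero-reduction, which cannot count as cure under 8 months. Missing results count as failures (SAP 4.3), which could shift stratum rates either way. This also stands: the size and even the direction are unknown. Direction, though, does not decide the matter, since the stratified interval is narrower whether infants do better or worse.

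The largest gains need a steep gradient and 38 children in each infant stratum, a target that need not be met. In four of the six scenarios the continuity term (0.0075) adds more width than pooling does (0, 0.0011, 0.0055 and 0.0018). That is a fair limit on the size of the point, but it does not justify leaving out the stratification factor.

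Timing is a further limit. A Part 2 investigator meeting had already been held in April 2019, so Part 1 may be complete. The documents do not say whether it is unblinded.

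**Conclusion.** The point holds in its conditional form: the planned interval ignores the randomisation strata and is wider than it need be whenever cure rates differ by age. Under the assumed rates, the reduction available in half-width before the continuity term is 0% if rates are flat, about 1% with a mild gradient or if infants do somewhat worse, and 5% to 15% with moderate to steep gradients at 38 per stratum. With 30 to 40 infants in strata 1 and 2 combined, that last range becomes about 2% to 11%.

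These figures rest on assumed stratum rates, a constant 15-point loss for the power values, and normal approximations. The steepest case should not be read as the expected one. This is an improvement to consider, not an error that invalidates the comparison, and confidence in its practical size is moderate.

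**What to change.** In SAP 6.2.1.1:

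- Make the main 60-day versus 30-day estimate the Mantel-Haenszel common risk difference over the randomisation age strata, with its stratified 95% CI (PROC FREQ on stratum by group by cured, common risk difference). Apply the existing decision rule to that interval, and state the variance used and whether a continuity term applies.
- Prespecify merging of sparse strata, for example merging adjacent strata, 1 with 2 first, if either arm has fewer than 5 subjects in one. Say what follows if the merged stratum is still sparse, since the next merge crosses 8 months, where the cure definition changes.
- Keep the pooled difference as supportive and the by-stratum differences as planned.
- Use the same method at Visits 3, 6, 8 and 10. Keep an exact CI where cures are very few, with the threshold set in advance.
- If Part 1 is already unblinded, leave the planned analysis as it is and add the stratified estimate as a labelled supportive analysis.

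The cost is a few lines of SAP text and code. The strata are already in the IVRS/IWRS data, and no extra subjects or measurements are needed. The downsides are coverage slightly below nominal, the need for a merging rule, and no gain if cure rates turn out flat across age.
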